The goal of this module is to exercise 5 days/week, for at least 30 min each day, of moderate intensity⁴⁷. Participants complete the Exercise Questionnaire each session to track their exercise. We begin this module by discussing the importance and rationale for exercise. We review evidence that exercise is particularly important in enhancing mood. We also discuss ways of increasing *lifestyle activity* (i.e., taking the stairs, standing instead of sitting, walking to the store). In this way, we approach exercise as a task not requiring sustained or extreme energy, concentration, and motivation, but a more casual experience, which can last for a relatively short period of time and still be helpful. This paradigm shift in conceptualizing exercise as lifestyle activity is very important for individuals who have a vulnerability to think negatively about themselves, their world, and their future. We utilize CBT strategies to challenge negative thoughts about exercising, which for individuals with BD is often their most significant obstacle^{44, 48}. We also set weekly exercise goals and discuss participants’ obstacles to adhering to these goals. Many exercise programs encourage participants to find a “work out partner”⁴⁵. This can be especially problematic for individuals with BD who tend to isolate when depressed or have interpersonal problems when manic⁴⁸. Given that social support is still a very important motivator and can buffer against future episodes^{49, 50}, we discuss the concept of “structured, group lifestyle activities.” Feedback from our pilot groups suggests that this is immensely helpful, even participants with anxiety report that they can tolerate *structured* groups as they do not feel pressure “to perform” or “to interact with others.” Some participants from our pilot group have noted that exercising when manic helps them to stay focused and keep their energy level down, while others have reported the opposite effect. Similarly, some participants reported choosing to exercise in the evening as it helps them to relax and sleep, while others report needing “wind down time” after exercising. By including individuals with manic symptoms, we will learn more about the association of exercise and mania.

C. Wellness Module

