Currently there are no theoretically integrated treatments for the medical burden associated with BD. This is enormously problematic given the increased risk that this medical burden poses for this population’s course of illness, functioning, and morbidity. Given the scope of the problem and lack of treatments, leaders in the field have called for further treatment development^{14, 15}. Proposed as 18 sessions (45-60 minutes each) over 20 weeks in an individual therapy format, NEW Tx is composed of the following treatment modalities: Nutrition/weight loss, Exercise, and Wellness treatment. A blinded independent evaluator will be used to administer assessments (see Table 1) and an unblinded study coordinator will oversee recruitment and scheduling. As will be described in detail in the following sections, the research study will utilize the intervention modules in two distinct pilot samples:

- i. **Phase I:** In the first phase of the study, we will test NEW Tx in a nonrandomized, open trial ($n = 6$). This pilot group for NEW Tx will be used to test the feasibility of the treatment as determined by participant attendance, therapist adherence to the procedures, and client feedback. All participants in this initial sample will be treated by the Principal Investigator (PI).

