An EKG will be required for participants over the age of 40, if clinically indicated, to further minimize potential risks associated with exercising. For clinical monitoring and assessment of adverse events, a fasting blood draw will be conducted at Week 0, Week 10, and Week 20. For the waitlist group (i.e., TAU participants who choose to receive NEW Tx after 20 weeks), fasting blood draws will be conducted at Weeks 30, Week 40, and Week 52, in addition to the aforementioned draws. Drug screens will not be required; however, administration of drug screening as part of ongoing treatment is at the discretion of the treating physician at any time after consultation with the participant.

C. Diagnostic and Clinical Assessments

- i. **Extended Mini-International Neuropsychiatric Interview** (MINI⁵⁷) will be used to establish DSM-IV diagnoses including BD, substance use, and eating disorders.
- ii. **Demographics, Medical History, and Psychiatric History** forms will assess any pertinent medical or psychiatric conditions that may impact the participants' eligibility or treatment in this study.
- iii. **Montgomery Asberg Depression Rating Scale** (MADRS⁵⁸) is a 10-item clinician-rated measure of depression that assesses the presence and severity of patient's current depressive symptoms.
- iv. **Young Mania Rating Scale** (YMRS⁵⁹) is an 11-item, clinician-rated measure that assesses the presence and severity of patient's current symptoms of mania.
- v. **Clinical Global Impression-Bipolar Illness** (CGI-BP⁶⁰) is a one item illness severity score that is a widely accepted, reliable, and valid assessment of global illness in BD⁶¹. The CGI-BP is a modified version of the CGI designed specifically for use in assessing global illness severity in patients with BD. This version assigns ratings for mania, depression, overall severity, and side effects.
- vi. **Clinical Monitoring Form** (CMF) Medication Module⁶² will track medication and dosage changes and whether the subject is taking medications for blood pressure (used to calculate the FSR score).
- vii. **Food Diaries** or a self-report record of foods and calories consumed will be completed by participants between study visits as needed. Selected food diaries will be reviewed by a dietitian (as needed).

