ET= Early Termination. Vitals = Height (at Week 0 and Week 20), weight, waist circumference, blood pressure, pulse, and Dual X-Ray Absorptiometry (i.e., body composition). ** Includes lipid profile (i.e., cholesterol, triglycerides), metabolic panel (i.e., blood urea nitrogen (BUN), creatinine (Cr), electrolytes, blood glucose level), complete blood count (CBC), and thyroid stimulating hormone (TSH). C reactive protein (CRP) and inflammatory marker panels (Human TH1/TH2 10-Plex (IFN-g, IL-1b, IL-2, IL-4, IL-5, IL-8, IL-10, IL-12p70, IL-13, TNF-a)) will be included at pre- and post-treatment visits. A urine pregnancy test will be administered at Week 0 to determine eligibility. An EKG will be completed at Week 0 for participants \geq 40-years-old, if clinically indicated.

¹As needed.

†For the TAU group, will only be collected at Weeks 0, 10, and 20

Table 2. Schedule of Assessments for the Waitlist Group (TAU participants who choose to receive NEW Tx)Weeks	21	22	23	24	25	26	27	28	29	30	31	32	33	34	35	36	37	38	39	40	52
										Mid-tx									Post-tx	Follo w-up	
CGI-BP										x									x	x	
Blood Draw**										x									x	x	
Vitals										x									x		
DXA scan																			x		
CMF										x									x	x	
MADRS										x									x	x	
YMRS										x									x	x	
LIFE-RIFT										x									x	x	
NEW Tx Scale																			x	x	
CSQ-8																			x	x	
URICA	x																		x	x	
Met Cart	x																		x		
Post-Tx Questionnaire																			x	x	
EQ	x	x	x	x	x	x	x	x	x	x	x	x	x	x	x	x	x	x	x	x	
Intent-to-Attend	x	x	x	x	x	x	x	x	x	x	x	x	x	x	x	x	x	x	x	x	
Food Diaries	x ¹																				

ET= Early Termination. Vitals = weight, waist circumference, blood pressure, pulse, and Dual X-Ray Absorptiometry (i.e., body composition). ** Includes lipid profile (i.e., cholesterol, triglycerides), metabolic panel (i.e., blood urea nitrogen (BUN), creatinine (Cr), electrolytes, blood glucose level), complete blood count (CBC), and thyroid stimulating hormone (TSH). C reactive protein (CRP) and inflammatory marker panels (Human TH1/TH2 10-Plex (IFN-g, IL-1b, IL-2, IL-4, IL-5, IL-8, IL-10, IL-12p70, IL-13, TNF-a)) will be included at pre- and post-treatment visits. A urine pregnancy test will be administered at Week 0 to determine eligibility.

¹As needed.

D. Independent Evaluator Training

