There is a possibility that study patients will not improve from this treatment. During the study assessments, subjects may also experience some discomfort from discussing personal material and completing self-report questionnaires. Subjects may also experience some discomfort from the blood draw. Participants will be exposed to radiation from two DXA scans. The total amount of radiation exposure is equal to a whole body exposure of approximately 16 microSieverts. A microSievert is a unit of radiation dose. This amount of radiation is about the same as you would normally receive in 2 days from natural background sources from the earth and the sky. Participants will also participate in a metabolic cart assessment, in which a clear plastic canopy will then be fitted over the head and upper chest of the participants to collect the air the participant exhales for 15 minutes. Participants may experience some discomfort or anxiety.

There is a risk of breach of confidentiality and loss of privacy, which great care will be taken to prevent.

B. Protection Against Risks

We will take precautions to ensure that potential risks are minimized. All treatments will be provided by at least master-level mental health professionals with experience in CBT and mood disorders. NEW Tx therapists will be closely supervised by the PI. In the case of an emergency, the NEW Tx therapist will page the PI. If the PI is unavailable, the covering clinician will be paged. If immediate assistance is required, the participant will be directed to call 911 or go to the MGH Acute Psychiatric Service. The following procedures will also ensure participant safety:

- i. All participants who fail to respond to treatment or withdraw prematurely will be referred for alternative treatment. If withdrawal from the study is necessary, we will provide appropriate referrals for other treatment. The PI, or the covering clinician, will be available to discuss the study, alternative treatments, or any concerns about the study with subjects if requested by the participant, therapist, or independent evaluator.

- ii. Ratings on the MADRS suicide item will be monitored during the open trial (Phase I) and the randomized trial (Phase II). Participants' with a suicidality score greater than 4 at Week 0—for either trial—will be excluded from the study.

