- iii. Participants' NEW Tx therapists will be available to them to discuss any concerns throughout the treatment period. The PI, or a covering clinician from the MGH Bipolar Clinic and Research Program, will make every effort to be available at all times to study participants in the event of a clinical emergency. However, if immediate assistance is required, the participant will be directed call 911 or go to the MGH Acute Psychiatric Service which is open and staffed 7 days a week, 24 hours a day. Participants will be withdrawn from either the open trial (Phase I) or the pilot study (Phase II) if their clinical condition deteriorates substantially. Participants may also be withdrawn if, in the judgment of the study investigators, remaining in the study poses a substantial risk to the participant or a higher level of care is needed.

C. Ensuring Confidentiality

To ensure protection of confidential information, all data will be coded and stored in locked files in the MGH Bipolar Clinic and Research Program. Names will not be included in computerized data files or in any published reports. Case records will be reviewed only by study personnel or, if necessary, by institutional, state, or federal regulatory personnel. All research personnel will have completed the Collaborative Institutional Training Initiative (CITI) Program on-line training and final exam, be well versed in Health Insurance Portability and Accountability Act (HIPAA) regulations and procedures, and be approved as study staff by the IRB. All HIPAA guidelines will be followed and all research personnel will be educated about the importance of strictly protecting participants' rights to confidentiality.

VII. DATA COLLECTION

All data collection will adhere to HIPAA regulations. Data will be obtained specifically for research purposes and managed using the REDCap system. Data on feasibility and satisfaction of NEW Tx as well as medical burden, BD symptoms, and functioning will be collected via patient self-report, clinician- and rater-administered assessments. These data will be used to evaluate treatment feasibility and acceptability, treatment integrity, efficacy, and possible mechanisms of change. Data assessing safety and adverse events will be collected through blood analysis.

A. Safety and Monitoring

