There will be a Data Safety and Monitoring Board (DSMB) for this study composed of three investigators who have experience in clinical research, clinical treatment of BD, and specifically overseeing the safety of participants in bipolar trials. This DSMB will monitor safety issues, including the review of adverse events, the PI's quarterly report of the study's progress, all IRB amendments, the adequacy and integrity of accumulating data, and the capability of the Phase I and II trials to test the hypotheses. The purpose of this process is to assess scientific integrity and patient safety issues, and ensure the ethical conduct of the trials. The DSMB will approve the initiation of the study and subject enrollment, and determine if study procedures should be altered or stopped due to evidence of benefit or harm to trial subjects that may be attributable to NEW Tx or reasons related to scientific integrity. The PI will submit quarterly reports to the DSMB detailing any study changes, adverse events, subject recruitment and retention, reasons for early termination, and ongoing data reports. The PI will also respond to all DSMB issues and queries.

B. Adverse Events

Any serious adverse events (e.g., death, suicide attempt, hospitalization) will be reported within 24 hours to the IRB and the NIMH program officer. A full written report of the event will be sent to the above entities within 10 working days of the event's occurrence. All adverse events will be assessed for the events' severity/intensity, expectedness, relatedness to NEW Tx, clinical outcome, and any action taken due to the event. Any adverse event (e.g., causing interference with usual activities or requiring treatment) and which appears definitely, probably, or possibly related to study participation will be tracked and reported to the IRB at the yearly continuing review. Any serious adverse events will be summarized in the NIMH, DSMB, and IRB annual progress reports. We will also inform the NIMH, DSMB and the IRB of actions, if any, as a result of their continuing review.

VIII. DATA ANALYSIS

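### Section VII names blood analysis as the source of adverse-event data, and nothing in the plan asks about injury, hospitalization or other clinical events in either arm

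*Combined protocol and SAP*

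**What the plan says.** All references are to the combined protocol and SAP.

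- **Source of the data.** Section VII: "Data assessing safety and adverse events will be collected through blood analysis". IV.B gives the draws the same purpose: "For clinical monitoring and assessment of adverse events, a fasting blood draw will be conducted at Week 0, Week 10, and Week 20".
- **What must be assessed and reported.** VII.B: "Any serious adverse events (e.g., death, suicide attempt, hospitalization) will be reported within 24 hours to the IRB and the NIMH program officer". It also requires every adverse event to be assessed for severity, expectedness, relatedness to NEW Tx, outcome and action taken. Events judged at least possibly related to taking part are tracked for the yearly IRB review.
- **What is measured outside the blood tests.** IV.C lists the MADRS, the YMRS and a CGI-BP that includes a side-effects rating. Table 1 schedules them before, midway through and after treatment and at follow-up, for both groups. Table 2 does the same at Weeks 30, 40 and 52 for the waitlist group. VI.B says the MADRS suicide item is monitored in both phases.
- **Contact.** IV.A describes NEW Tx thus: "Proposed as 18 sessions (45-60 minutes each) over 20 weeks in an individual therapy format". A Table 1 footnote on the Intent-to-Attend and Food Diaries rows reads: "For the TAU group, will only be collected at Weeks 0, 10, and 20".
- **Analysis.** Section VIII contains no between-arm comparison of adverse events.

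**The concern.** VII.B covers what happens once an event is known. It does not say who asks about events, when, or in what words. The only stated route, blood analysis, cannot reveal an injury in an exercise programme, a hospital admission or a suicide attempt. Followed literally, the plan would miss events that VII.B obliges the investigator to assess or report.

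In practice clinical events will probably surface because a participant mentions them. That introduces a second problem: the arms do not have the same number of occasions on which to mention anything. VII.A asks the DSMB to judge whether procedures should change because of harm attributable to NEW Tx. That judgement is weaker if the TAU event count partly reflects fewer conversations.

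**Working it through.** **Step 1: is there any elicitation route?** Section IV.C lists 19 instruments. Those closest to an adverse-event inquiry are:

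- The medical and psychiatric history forms and the PAR-Q, which Table 1 schedules at Week 0 only.
- The CMF Medication Module, which tracks medication and dose.
- The LIFE-RIFT, which measures functioning.
- The MADRS and YMRS, which rate current symptoms.
- The CGI-BP, which includes a side-effects severity rating.

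None asks whether an injury, admission or other event has occurred since the last visit. No row of Table 1 or Table 2 adds such a question.

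**Step 2: scheduled contacts to Week 20.** Table 1 has columns for Weeks 0 to 14 (15 columns) plus Weeks 16, 18 and 20, which gives 15 + 3 = 18 and matches the 18 sessions in IV.A. Excluding Week 0 leaves 17. For TAU, the footnote implies Weeks 0, 10 and 20, so 2 post-baseline contacts. This is an inference, because the footnote is attached to two rows only. The Exercise Questionnaire row runs through every column without a TAU exception, although III.B ties it to sessions: "Participants complete the Exercise Questionnaire each session to track their exercise".

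- Ratio of contacts: 18/3 = 6.0 including Week 0; 17/2 = 8.5 after baseline.
- Longest gap: 2 weeks against 10 weeks.
- Mean wait from an event to the next contact, for events spread evenly over 20 weeks, is the sum of (gap²/2) divided by 20. NEW Tx has 14 gaps of 1 week and 3 of 2 weeks: (14 × 0.5 + 3 × 2)/20 = 0.65 weeks. TAU has 2 gaps of 10 weeks: (2 × 50)/20 = 5.0 weeks.

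**Step 3: illustration of unequal capture.** Assumptions, none of them from the documents: equal true risk, events spread evenly over 20 weeks, no detection outside these contacts, and an event mentioned at the next contact if still recalled, with recall halving every h weeks. Then

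capture = (1/20) × (h/ln 2) × Σ(1 − 2^(−gap/h)).

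For h = 2, h/ln 2 = 2.885. NEW Tx: [14 × (1 − 0.7071) + 3 × (1 − 0.5)] × 2.885/20 = 0.808. TAU: 2 × (1 − 0.03125) × 2.885/20 = 0.280.

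| Recall half-life (assumed) | NEW Tx capture | TAU capture | Ratio |
|---|---|---|---|
| 2 weeks | 81% | 28% | 2.9 |
| 4 weeks | 90% | 48% | 1.9 |
| 8 weeks | 95% | 67% | 1.4 |
| 16 weeks | 97% | 81% | 1.2 |

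**Step 4: in event counts.** Assume a true risk of 30%. With 30 per arm (IV.A gives 60 in Phase II) there are 0.30 × 30 = 9 true events per arm. Recorded events would be 7.3 against 2.5 at a 2-week half-life, and 8.8 against 7.3 at 16 weeks. With 20 per arm (Section II gives 40) there are 6 true events per arm, recorded as 4.8 against 1.7 and 5.8 against 4.9.

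**Step 5: where the illustration does not apply.** The MADRS, YMRS and CGI-BP are scheduled at the same visits in both arms, and IV.A assigns assessments to a blinded evaluator. Extra therapist contact does not create unequal opportunity for those scheduled ratings.

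**The case against.** The strongest reply is that the Section VII sentence is loosely worded and the trial plainly does more than draw blood. Much of that stands. A reader might infer that suicidality and mood switch go undetected. The documents do not support this: suicidality, mania and side-effect severity are rated in both arms on a shared schedule. In particular, the remark in III.B that exercise while manic helped some pilot participants and had the opposite effect in others does not show biased detection, because mania is rated with the YMRS at common visits. What remains is narrower. The MADRS and YMRS rate current symptoms, so an episode or attempt that has resolved before the visit need not appear, and nothing says when a score becomes an adverse event.

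It can also be said that, if blood were truly the only route, detection would be equally poor in both arms. That is correct. The asymmetry is conditional on spontaneous reporting, and no section gives NEW Tx therapists an adverse-event question either. TAU participants also have routine care whose frequency is not stated, and VI.B makes the investigator or a covering clinician available to all participants.

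A reader might infer a larger distortion. A hard recall cut-off of 2 to 6 weeks gives TAU coverage of 2 × 2/20 = 20% to 2 × 6/20 = 60%, hence ratios of 5 to 1.7. That range needs complete capture in NEW Tx and an abrupt loss of recall, so it is not a sound estimate.

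Finally, this is a feasibility pilot with no planned between-arm adverse-event analysis. That limits the consequence, but it does not supply a way for events to become known.

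**Conclusion.** The gap is real and should be fixed. The stated method of collecting adverse events cannot find clinical events that VII.B requires to be assessed or reported, and no form or schedule entry fills the gap. Injury has no instrument at all. Hospitalization and suicide attempt have a reporting rule but no stated route of discovery.

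Unequal detection is a conditional risk. If events surface mainly by spontaneous report, NEW Tx could look less safe with no true difference, by about 1.2-fold (16-week recall half-life) to 2.9-fold (2-week). The direction is the same throughout that range. The size rests on assumed recall, on a TAU schedule inferred from a footnote, and on no other TAU detection. It does not apply to the scheduled mood ratings. VII.B may add to the tilt, because relatedness is judged against NEW Tx and the yearly IRB tracking covers only events judged related to participation.

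A reader might infer that a planned safety comparison is invalid. No such test exists in Section VIII. The consequence falls on descriptive safety reporting and on what the DSMB sees.

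**What to change.** 1. Replace the Section VII sentence so that it agrees with IV.B, VI.B and VII.B: safety data come from blood analysis, from the MADRS, YMRS and CGI-BP ratings, and from a clinical adverse-event query.
2. Add one fixed query on injury, hospitalization and any other adverse event since the last assessment, with the same wording in both arms, at Weeks 10, 20 and 32 (Weeks 30, 40 and 52 for the waitlist group). Add it as a row in Tables 1 and 2.
3. Record every reported event whatever its judged relatedness.
4. Base any between-arm description on these scheduled reports. Restrict it to the period up to Week 20, since TAU participants may take up NEW Tx after that.
5. Tabulate events volunteered at NEW Tx sessions separately, and still report them under VII.B.

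The cost is one short form at visits already held, plus the wording. If the blinded evaluator asks the query, it should follow the ratings, because an answer may reveal the arm. The main downside is recall over intervals of 10 weeks or more. In the illustration above, a common query at Weeks 10 and 20 gives a capture ratio of 1.0, but each arm's scheduled reports would capture only 28% to 81% of events. The query makes the arms comparable; it does not make capture complete, which is why volunteered events must still be kept.

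### The plan secures no record of non-serious adverse events that is independent of judged relatedness and collected alike in NEW Tx and TAU

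*Combined protocol and SAP*

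**What the plan says.** Section VII.B (Adverse Events) uses two relatedness criteria in consecutive sentences.

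- Assessment: "All adverse events will be assessed for the events" severity, and then for "expectedness, relatedness to NEW Tx, clinical outcome, and any action taken due to the event". This has no limit by arm or by relatedness.
- Tracking: the sentence covers an adverse event "which appears definitely, probably, or possibly related to study participation will be tracked and reported to the IRB at the yearly continuing review". The criterion here is taking part in the study, not receiving NEW Tx.

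Serious events are handled separately and without a relatedness filter: "Any serious adverse events (e.g., death, suicide attempt, hospitalization) will be reported within 24 hours to the IRB and the NIMH program officer", and "Any serious adverse events will be summarized in the NIMH, DSMB, and IRB annual progress reports".

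Section VII.A adds: "The PI will submit quarterly reports to the DSMB detailing any study changes, adverse events, subject recruitment and retention". That report has no relatedness filter either. The same section lets the DSMB decide whether procedures should be altered or "stopped due to evidence of benefit or harm to trial subjects that may be attributable to NEW Tx".

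On ascertainment, the opening of section VII names blood analysis as the route for safety and adverse event data and gives no other. Table 1 applies to both arms. It has rows for bloods, vitals, MADRS, YMRS and CGI-BP but none for adverse events. Section VIII contains no safety summary.

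**The concern.** A randomised control arm lets harm be judged by comparing event rates, without deciding case by case what caused each event. That works only if events are recorded in both arms whatever their presumed cause and are looked for in the same way.

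VII.B promises to assess every event, but its only explicit promise to track a non-serious one depends on judged relatedness. No sentence says that a non-serious event judged unrelated is kept. The plan does not say how relatedness to NEW Tx is to be rated in a TAU participant during Weeks 0–20, or who rates it.

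This matters because participants must be currently ill (IV.B), so a mood episode is easily put down to the underlying disorder. Section III.B also treats the link between exercise and mania as open. Some pilot participants said that "exercising when manic helps them to stay focused and keep their energy level down, while others have reported the opposite effect". That remark concerns focus and energy and is not evidence of harm, but it shows why an attribution-free record would be useful.

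**Working it through.** The documents give no adverse event rate and no safety sample size or power, so there is no figure of the plan's to reproduce. The check has three parts.

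**1. What is secured for each type of event, from the text.**

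- Serious events: reported and summarised whatever the relatedness or arm (VII.B). No gap.
- Laboratory changes, blood pressure, and mood state at assessment visits: scheduled in both arms (Table 1), with a blinded evaluator for assessments (IV.A). MADRS and YMRS changes are compared by arm (VIII.B), and MADRS suicide-item ratings are monitored in Phase II (VI.B). No gap at those visits.
- Non-serious events outside those measures, such as injuries or mood episodes that resolve between Weeks 0, 10 and 20: to be assessed, but tracked explicitly only if judged related. No common elicitation is described. NEW Tx has 18 therapy sessions in 20 weeks (IV.A) at which an event can come up, and the plan describes no equivalent contact for TAU. This is the gap.

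**2. What a relatedness filter could do (illustration; the event rates and pass shares are assumptions).**

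The number per arm at 1:1 allocation is 40/2 = 20 from the Specific Aims, or 60/2 = 30 from IV.A and IV.B. The documents give both totals.

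Expected tracked events in an arm = n × p × f, where p is the true event rate and f the share passing the filter. Apparent risk difference = p(NEW)·f(NEW) − p(TAU)·f(TAU). Counts below are for 30 per arm.

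- Equal true rates of 20%, with 50% of NEW Tx and 0–10% of TAU events passing: 30 × 0.20 × 0.50 = 3.0 v 30 × 0.20 × (0 to 0.10) = 0 to 0.6. Apparent excess: 0.10 − (0 to 0.02) = 8 to 10 points, when the truth is 0.
- Equal true rates of 40%, same shares: 6.0 v 0 to 1.2. Apparent excess: 0.20 − (0 to 0.04) = 16 to 20 points.
- Equal true rates of 20%, with 50% passing in both arms: 3.0 v 3.0, difference 0. The spurious excess comes from unequal pass shares.
- True rates 40% v 20%, with 25% passing in both arms: 30 × 0.40 × 0.25 = 3 v 30 × 0.20 × 0.25 = 1.5. Apparent difference: 10% − 5% = 5 points, against a true 20 points (12 v 6 events).

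The apparent differences do not depend on n and are the same with 20 per arm. The filter can create an excess or shrink a real one.

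**3. Precision with complete capture.**

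Power, two-sided alpha 0.05, normal approximation with pooled variance under the null, for 40% v 20%:

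- 30 per arm: (0.20 − 1.96 × √(2 × 0.3 × 0.7/30)) / √((0.4 × 0.6 + 0.2 × 0.8)/30) = (0.20 − 0.232)/0.115 = −0.28, so 39%.
- 20 per arm: (0.20 − 0.284)/0.141 = −0.59, so 28%.

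With no events in an arm, the one-sided 95% upper bound is 1 − 0.05^(1/n): 9.5% for 30 and 13.9% for 20.

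**The case against.** The strongest reply is that the tracking sentence sets what goes to the IRB each year and does not say that other events are discarded. The sentence before it requires every event to be assessed for severity, outcome and action taken, which is hard to do without a record. TAU participants also take part in the study: Table 1 schedules the same blood draws, DXA scans, metabolic cart and interviews for them, so their events can meet the study-participation criterion. This stands, and it makes the problem an unsecured record rather than a stated rule to throw events away.

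A reader might go further and infer that only related events are kept, that TAU has no comparable record, that TAU counts are near zero by construction, or that the DSMB cannot judge harm. The documents support none of these. Serious events bypass the filter, the DSMB receives adverse events quarterly without it, and much of what matters clinically is measured on schedule in both arms. A TAU pass share of zero is an assumption, not a finding. Nor do the documents say that relatedness is judged with knowledge of the arm, although rating relatedness to NEW Tx is hard to do without it.

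It can also be said that a pilot of this size could not compare harms precisely under any recording rule. That is true, but imprecision is no reason to leave recording dependent on attribution. The unfiltered quarterly report does not close the gap either, because it can contain only what was recorded and nothing says it is split by arm.

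**Conclusion.** This is a cheap improvement to the plan, not a defect that undermines the trial. For non-serious events not caught by the scheduled scales, vitals and bloods, the plan does not secure a record that is independent of attribution and gathered in the same way in both arms. It also uses two relatedness terms without reconciling them. A comparison of such events between NEW Tx and TAU may therefore be biased in either direction.

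The size cannot be computed from the documents. The 8 to 20 point spurious excess and the shrinkage from 20 to 5 points rest wholly on assumed rates and pass shares, and they show direction and mechanism only. Even with full and equal capture, power for 40% v 20% would be 28% to 39% with 20 to 30 per arm.

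**What to change.** In VII.B:

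- Record every adverse event in both arms, whatever the judged relatedness. Keep relatedness as a recorded field under one reconciled term, and state how it is rated for TAU in Weeks 0–20.
- Elicit events with the same question at the assessment visits that both arms share (Weeks 0, 10, 20 and follow-up), and add an adverse event row to Table 1. Mark events first noted at a therapy session, so that the extra contact in NEW Tx can be separated out. Recording everything without equal elicitation would not make the arms comparable.
- In the existing quarterly DSMB report, tabulate non-serious and serious events by randomised arm for Weeks 0–20. After Week 20, TAU participants may take NEW Tx.
- Apply the relatedness filter only to the yearly IRB report.

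The cost is protocol wording and more minor background events to enter in REDCap. No extra visits, staff or patients are needed.
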